3.2 Primary Safety Endpoints

- CBC with differential, actual values and percent change in values from Screening visit to Week 12 visit.
- CMP (Na, K, Cl, CO2, BUN, Cr, Ca, Mg, Ph, glucose), actual values and percent change in values from Screening visit to Week 12 visit.
- LFTs (Total bilirubin, AST, ALT), actual values and percent change in values from Screening visit to Week 12 visit.
- TSH, actual value and percent change in value from Screening visit to Week 12 visit.
- Vital signs (weight, height, blood pressure, and heart rate), actual values at each time point measured and percent change in values from Baseline to Week 12 visit (the end of the active treatment phase)
- Physical Examination, general assessment of health at Screening visit and at Week 12 visit (the end of the active treatment phase)
- Mean (%) relative abundance of microbial phyla and genera in fecal samples at Baseline and Week 12.
- Percent change in Bacteroidetes to Firmicutes (B:F) ratio in fecal samples from Baseline to Week 12.
- Change in alpha diversity ("within-sample") metrics (the absolute number of operational taxonomic units (OTUs), Chao1 estimator, and Shannon index) in microbiota from Baseline to Week 12.
- Change in beta diversity ("between-sample") metrics (Bray-Curtis dissimilarity, Weighted Unifrac distance, and Unweighted Unifrac distance) in microbiota from Baseline to Week 12.

4 Subject Selection and Withdrawal

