A Phase I study of orally administered SF- and GR-containing BSE (75 μ mol glucosinolates, 300 μ mol glucosinolates, or 75 μ mol isothiocyanates daily) for 7 days in 12 healthy volunteers did not demonstrate any clinical adverse events [51]. Two of 12 subjects assigned to active treatment demonstrated an increase in plasma ALT exceeding the upper limit of normal, though ALT levels rose for all subjects during the course of the study (including those assigned to placebo control), and the increase was not clearly attributable to consumption of BSE. Three of 12 subjects (2 active treatment, 1 placebo) demonstrated TSH levels exceeding the upper limit of normal during or after the dosing period, though elevated TSH was not associated with clinical symptoms or T3/T4 abnormalities.

Egner et al. [46] conducted a cross-over trial in 50 participants, randomized to ingest a SF-rich beverage (150 μ mol/day) for 7 days in a first or second phase. Two of 50 participants complained of bitter taste or nausea, and no other adverse events were reported. No abnormal serum chemistry values were reported after 7 days. In a study of healthy participants ingesting a beverage containing 600 μ mol of glucoraphanin and 40 μ mol of sulforaphane, the intervention was well-tolerated with no laboratory evidence of effect on liver and kidney function [43].

A study of orally administered broccoli sprout homogenates (25 to 300 g) in 57 subjects over 3 separate days found no adverse effects aside from mild digestive effects [98]. Similarly, in a RCT of 20 men with recurrent prostate cancer treated with sulforaphane 200 μ mol/ day for 20 weeks, no serious adverse events occurred, though some reported mild gastrointestinal upset [40].

A randomized, placebo-controlled trial of the sulforaphane product Prostaphane[®] in 81 men with rising prostate specific antigen (PSA) values following radical prostatectomy for prostate cancer represents the highest daily dosing of sulforaphane to date (338 µmol) [99]. No serious adverse events were reported, though gastrointestinal bloating was experienced somewhat more often in the SF group (N=17 vs. N=10), and one participant in the SF group withdrew from the study due to bowel discomfort. The differences in adverse effects between the two groups were not statistically significant (p=0.149). Furthermore, no significant between-group differences were found for body weight, BMI, blood counts, and chemistries.

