If the dose is reduced during the course of the study, the participant will continue the lowered dose for the remainder of the study. If adverse events do not improve within 14 days of lowering the dose, the investigational product may be permanently discontinued at the discretion of the treating study physician, participant, and participant's guardian. If a participant exhibits extreme exacerbation of behavioral symptoms (such as self-injurious behavior or aggression) that do not improve substantially following a dose reduction and are determined "probably" or "definitely" related to taking the investigational product, the investigational product may be permanently discontinued sooner than 14 days post-reduction, and the DSMB will be notified. As individuals with ASD often have cyclical changes in behavior independent of medication effects, the study staff will rely on caregivers' experience with the participant to determine if any observed behavior changes are within the expected range for that individual. If the investigational product is stopped permanently, the participant and his caregiver will be asked to complete the remainder of the study visits, return any unused study drug, and repeat safety lab studies.

2 Study Objectives

Primary Objective:

The primary objective of this clinical trial is to determine if Avmacol[®] is superior to placebo for improving social communication impairment in adolescent and young adult men with moderate to severe autism spectrum disorder (ASD), as measured by change in Social Responsiveness Scale-2 (SRS-2) [100] total scores.

Secondary Objectives:

Secondary objectives include: (1) assessing the safety and tolerability of Avmacol[®] in subjects with ASD; and (2) characterizing the effects of Avmacol[®] on behavioral challenges commonly associated with ASD, including hyperactivity, irritability, repetitive behavior, and inappropriate speech.

Exploratory Objectives:

In a subset of 30 participants, exploratory objectives include: (1) Assessment of gut micobiota diversity and relative abundance of microbial species from fecal samples collected before and after 12 weeks of treatment with sulforaphane or placebo. (2) Explore the relationship between changes in microbiota composition and behavioral outcomes in young men treated with sulforaphane or placebo.

3 Study Design

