• Unexpected in nature, severity, or frequency (i.e. not described in study-related documents such as the IRB-approved protocol or consent form, the investigator's brochure, etc.),

• Related or possibly related to participation in the research (i.e. possibly related means there is a reasonable possibility that the incident experience, or outcome may have been caused by the procedures involved in the research,

• Serious (as defined below) "Serious" is different than "severe" as reported in the CTC criteria that applies a grade to the AE.

2. An adverse event (AE) is any symptom, sign, illness or experience that develops or worsens in severity during the course of the study. Intercurrent illnesses or injuries will be regarded as adverse events. Abnormal results of diagnostic procedures (eg, laboratory values) are considered to be adverse events if the abnormality:

- results in study withdrawal
- is associated with a serious adverse event
- is associated with clinical signs or symptoms
- leads to additional treatment or to further diagnostic tests
- is considered by the investigator to be of clinical significance
- **3.** A serious adverse event is any AE that is:
- fatal
- life-threatening
- requires or prolongs hospital stay
- results in persistent or significant disability or incapacity
- a congenital anomaly or birth defect

• an important medical event (of major clinical significance and may require intervention to prevent one of the serious outcomes noted above)

All adverse events that do not meet any of the criteria for serious will be regarded as *non-serious adverse events*.

b. Monitoring of adverse events: The study physician will review AEs with the participant and family member at each study visit (baseline, week 2, week 4, week 8, week 12, week 16), and patients and their families will have 24/7 access to the study PI or a designated covering physician by phone/ pager to report possible AEs as needed between visits. AEs will be recorded on an AE log and assigned a numerical grade of 0 (not at all a problem), 1 (mild problem), 2 (moderate problem), and 3 (severe problem). As previously noted, an AE rated as severe ("3") is distinct from classification of a serious AE, defined above. The study period during which adverse events must be reported is defined as the period from the initiation of any study procedures to the end of the study treatment follow-up. For this

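### Section 3.2 names no adverse event, seizure, dose-reduction or discontinuation endpoint and Section 7 has no safety analysis, so tolerability has no endpoint and safety is only partly covered

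*Combined protocol and SAP*

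**What the plan says.** Section 2 gives, as the first secondary objective, "assessing the safety and tolerability of Avmacol[®] in subjects with ASD". The Study Summary states the same aim.

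Section 3.2 lists ten primary safety endpoints. Four are laboratory items (CBC, CMP, LFTs, TSH), of which the liver item is typical: "LFTs (Total bilirubin, AST, ALT), actual values and percent change in values from Screening visit to Week 12 visit". Vital signs, including weight, are taken as "actual values at each time point measured and percent change in values from Baseline to Week 12 visit". Physical examination is the sixth. The other four are microbiota measures, beginning with "Mean (%) relative abundance of microbial phyla and genera in fecal samples at Baseline and Week 12". Section 2 places the microbiota aims elsewhere: "In a subset of 30 participants, exploratory objectives include".

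AEs are dealt with outside the endpoint list. Section 3.1 has them monitored at every visit and at the Week 2 call, and Sections 8.1 and 8.2 define and record them. Appendix 6B, part V.b, says: "AEs will be recorded on an AE log and assigned a numerical grade of 0 (not at all a problem), 1 (mild problem", and so on up to 3 for a severe problem. Section 8.5 sets rules for reducing or stopping treatment, and Section 8.6.1 and Appendix 6B set out DSMB review.

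Section 7.2 describes analyses of the SRS-2, CGI-Severity, RBSR and microbiota, and none of safety. Section 7.3 defines one analysis population: at least one dose and at least one post-baseline efficacy assessment.

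**The concern.** An endpoint list tells the analyst what the trial report must compare. Here the list omits the events by which tolerability is normally judged and most of the harms the protocol itself raises. A report that followed Sections 3.2 and 7 to the letter could describe safety without setting the arms side by side on gastrointestinal symptoms, seizures, SAEs, dose reductions or stops. Any such comparison would have to be devised after the data were seen, and the choice of which AEs to show, and in whom, would be open. The population rule adds to this: a participant driven out early by an AE is the one whose data matter most for tolerability, and that participant can fall outside the only set defined.

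**Working it through.** **1. Each named harm against the endpoints and analyses**

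| Event | Where the protocol raises it | Where it is recorded | Endpoint in 3.1 or 3.2 | Analysis in Section 7 |
|---|---|---|---|---|
| Gastrointestinal symptoms | 8.1 | AE log | None | None |
| Seizure | Clinical Data to Date; 8.1 | AE log; 8.5 | None | None |
| SAE | 8.1 | AE log; 8.3 | None | None |
| Behavioural worsening | 1.4; 8.1; 8.5 | AE log; ABC | Indirect: ABC subscale change | None (7.2 does not name the ABC) |
| Dose reduction or permanent stop for an AE | 1.4; 8.5 | Drug accountability; 8.5 | None | None |
| Weight gain | 1.4; 8.1 | Vital signs | Yes, 3.2 | None |
| ALT or TSH above the limit | Clinical Data to Date | Screening and Week 12 bloods | Values and percent change, no count | None |

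Of the ten items in 3.2, 6 are laboratory, vital-sign or examination items, 4 are microbiota and 0 are AE measures.

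**2. Laboratory items**

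The Phase I signal that the protocol cites is a count of individuals: "Two of 12 subjects assigned to active treatment demonstrated an increase in plasma ALT exceeding the upper limit of normal". TSH exceeded its limit in 3 of 12 (2 active, 1 placebo). The same account says that ALT rose in all subjects, placebo included, and that the rise was not clearly attributable to the product.

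If percent change were summarised as an arm mean, 2 of 27 participants doubling their ALT, with no change in the other 25, would move it by 2 × 100 / 27 = 7.4 points. One rise of 500% would move it by 500 / 27 = 18.5 points.

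Percent change also ranks rises differently from a limit. Assume an upper limit of 40, a figure the documents do not give:

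- 15 to 30 is +100%, but only 30 / 40 = 0.75 times the limit.
- 78 to 121 is +55%, and 121 / 40 = 3.0 times the limit. The starting value is 78 / 40 = 1.95 times the limit, which the Section 4.2 example (exclusion above twice the limit) would admit.

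**3. Analysis population**

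The first post-baseline efficacy measures are at Week 4 (Section 6.5). The Week 2 call completes the AE log only (Section 6.4). A participant who takes the product, reports an AE at Week 2 and then leaves has AE data but no efficacy assessment, and is outside the 7.3 set. Each such participant is 1 / 27 = 3.7% of an arm.

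**4. What 27 per arm can show**

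The only sizing figure in Section 7.1 for the clinical outcomes is at least 80% power for the SRS-2 test. It concerns efficacy, and its stated inputs support it as a lower bound (96.4% by a noncentral F calculation with 15% loss spread over the visits). No size or precision is given for safety.

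- Zero events in n: one-sided 95% upper bound = 1 − 0.05^(1/n). For n = 27 this is 10.5%; the exact two-sided 95% interval ends at 12.8%. With 23 left after 15% loss, the figures are 12.2% and 14.8%. If the odd stratum size of 27 in Section 5.3 leaves unequal arms, the one-sided bound is 10.9% at 26 and 10.1% at 28.
- Chance of seeing at least one seizure in 27 = 1 − (1 − p)^27. At p = 1/29, the on-drug count in the earlier autism trial, this is 61%. It is 24% at 1% and 75% at 5%.
- Power to compare AE rates at 27 per arm (assumed rates, two-sided 0.05): 10% v 20%, 17%; 10% v 30%, 45%; 10% v 40%, 73%. About 10% v 43% is needed for 80%.

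One input needs reconciling. Section 1.4 puts the second seizure of the earlier trial in a participant taking placebo; Clinical Data to Date, Section 8.1 and Appendix 6B put it three weeks after stopping sulforaphane. The on-drug count of one is the same either way.

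**The case against.** The strongest reply is that safety is closely watched. AEs are sought by specific questioning at every contact, graded and logged, and Section 8.1 says when a laboratory abnormality becomes an AE. Seizures and related SAEs stop treatment and go to the DSMB, which also meets after every ten completers. All of that stands, so the gap is not in data capture. But oversight of individuals does not specify a comparison between arms for the report.

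Three stronger readings are tempting, and the documents do not support them.

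- A reader might infer that laboratory risk is scored only as percent change. The items say actual values as well, and never say that they will be averaged. What is missing is a count of out-of-range values.
- A reader might infer that no expected harm is compared at all. Weight gain is an anticipated effect and weight is in 3.2. ABC Irritability and Hyperactivity are secondary endpoints that can reflect worsening behaviour, though not as an AE count.
- A reader might infer that microbiota is being treated as evidence of safety. Sections 2, 7.1 and 7.2 consistently call it exploratory, and a sub-heading above those four items may have been lost when the text was extracted. At most they are misplaced.

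It is also fair that new AE endpoints would have little power. That argues for describing them with intervals, not for leaving them out.

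**Conclusion.** The point holds in this form. Tolerability, a stated objective, has no endpoint. Safety is partly covered by laboratory values, vital signs and examination, so it would be too strong to say that the safety objective cannot be answered. AE, SAE, seizure, dose-reduction and discontinuation data are collected but have no named endpoint and no by-arm analysis, and the only analysis set can exclude a participant who leaves before Week 4 because of an AE.

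The size is structural: none of ten listed safety endpoints concerns AEs, and Section 7 has no safety analysis. How many participants would leave before Week 4 is not given; Section 4.4.2 asks those who stop treatment to stay in follow-up, so the number may be small. The laboratory arithmetic is illustrative and rests on the assumed limit and on unchanged values in the other participants. The microbiota part is less certain, for the reason given above.

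**What to change.** In Section 3.2, add the following by arm, as proportions with exact 95% confidence intervals, described and not tested:

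- any AE whose log grade rises above its Baseline grade;
- the gastrointestinal symptoms named in Section 8.1;
- behavioural worsening recorded as an AE;
- seizures;
- SAEs;
- dose reductions and permanent stops for AEs.

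In Section 7.3, add a safety population of all participants who took at least one dose, and use it for these summaries.

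For ALT, AST and TSH, add the number above the upper limit at Week 12, tabulated by Screening status. A count only of moves from normal to high would miss participants who enter with ALT or AST between one and two times the limit and then rise, so show those who rise further as well.

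List the four microbiota items under exploratory endpoints, unless a lost sub-heading already does so.

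The cost is endpoint wording, a short paragraph in Section 7 and a few tables. No new procedure, visit or change in clinical management is needed. The intervals will be wide at 27 per arm, and the report should say so.

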Each tablet of Avmacol[®] contains 125 mg broccoli seed powder and 50 mg broccoli sprout extract, providing approximately 15 mg (34.4 µmol) of glucoraphanin and enough myrosinase to fully hydrolyze the glucoraphanin contained in the tablet. In the batch of tablets formulated for the proposed clinical trial, manufacturing specifications required at least 13 mg glucoraphanin per tablet, and recent analysis indicated 17 mg per tablet (see Avmacol[®] COA in Section 7). Manufacturing data from Nutramax, Inc. and bioavailability studies of similar compounds containing GR and myrosinase suggest a bioconversion to SF rate in the range of 40-50% [47]; it is expected that each Avmacol[®] tablet with therefore supply approximately 15 µmol SF following bioconversion. Exact amounts of bioavailable SF will varies somewhat from individual to individual depending upon endogenous enzymatic conversion following ingestion.

Healthy human volunteers ingesting 200 μ mol of SF from a broccoli sprout extract preparation demonstrated rapid absorption, first-order metabolism, and urinary excretion of metabolites (DTCs), yielding a mean half-life of 1.77 ± 0.13 hr. and volume of distribution of 59.9 ± 7.0 liters [57]. Despite the relatively short half-life, SF is believed to have a longer duration of action, as induced phase 2 enzymes have half-lives measured in days [56]. SF has been shown to cross the blood-brain barrier [58]. Urinary metabolites (DTCs) are renally excreted and can be quantified using a cyclocondensation reaction.

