4.4 Early Withdrawal of Subjects

4.4.1 When and How to Withdraw Subjects

Subjects will be withdrawn from *study* participation only if the subject or his legal authorized representative revokes consent for inclusion of subject data in group analyses.

Reasons for *treatment* withdrawal prior to the expected completion for a subject may include:

- The subject experiences a serious adverse event (SAE) that the study physician determines is likely related to the study treatment or that presents a safety risk for ongoing participation.
- The subject experiences a clinical seizure during the course of the active treatment phase, either by EEG confirmation or by strongly suggestive clinical history.
- The subject requires significant dose adjustments to concomitant psychopharmacological medications (e.g. stimulants, antidepressants, mood stabilizing agents, benzodiazepines) or starts a new psychopharmacological medication due to significantly worsened behavioral disturbance.
- The subject requires a new chronic medication that may potentially interact with the study medication.

No withdrawal symptoms or adverse effects are anticipated from abrupt discontinuation of the study medication. However, if a patient needs to discontinue the study treatment for one of the aforementioned reasons, every effort will be made to bring the subject in promptly for a clinic visit to perform safety measures, including physical examination and laboratory measures. As described below, study personnel will request that subjects who prematurely stop treatment complete the remaining study visits and procedures as outlined in the protocol.

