The week 12 visit marks the end of the active treatment phase of the study and will take approximately 2 hr. to complete. The patient and his caregiver will return to the clinic for a follow-up visit that will include measurement of vital signs (height, weight, blood pressure, heart rate, and temperature), physical exam by the study physician, and repeat blood draw for safety monitoring (CMP, LFTs, TSH, and CBC with differential). Caregivers will complete behavioral outcome measures (SRS-2, RBSR, and ABC), and clinicians will assign CGI-Severity and CGI-Improvement scores. At this phase-ending visit, responder status will be assigned to those with a 10 point or greater reduction on the SRS-2 and CGI-Improvement score of 1 or 2 (very much or much improved). Partial responder status will be assigned to participants with a 10 point or greater reduction on the SRS-2 and a CGI-Improvement score of 3 (minimally improved). The adverse event log will also be completed by the study physician. Caregivers will be asked to report any changes in concurrent medications or non-pharmacological treatments since the previous study visit. The medication log and returned tablets will be reviewed/ counted for treatment compliance, and any remaining investigational drug will be collected by study staff and returned to IDS for disposal. Participants will also return a stool sample in the OMNIGene-Gut stabilization kit. The kit will be labeled with the date and participant PIN, securely packaged in a Styrofoam container, and mailed to the Cullman Chemoprotection Center at JHU (director, [name]) for storage in cryovials at -80°C until all study samples have been collected.

6.8 Week 16 Follow-Up Visit/ Study Termination:

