8.5 Stopping Rules

• If a participant experiences significant adverse events that affect tolerability, may reasonably be related to taking the investigational product, and do not meet the protocol definition for a serious AE (including non-extreme behavioral changes), the dose may be reduced by approximately 30% according to the following dose modification schedule:

Weight category	Prescribed weight- based dose of glucoraphanin	Prescribed # of tablets	70% of weight-based dose (ie, 30% reduction)	Prescribed # tablets for reduced dose (rounded to nearest 15 mg increment)*
<100 lb	45 mg	3	31.5 mg	2
100-125 lb	75 mg	5	52.5 mg	3
126-175 lb	90 mg	6	63 mg	4
176-199 lb	105 mg	7	73.5 mg	5
≥ 200 lb	120 mg	8	84 mg	6

*Rounded down if equidistant between two 15 mg dosing increments

- If the dose is reduced during the course of the study, the participant will continue the lowered dose for the remainder of the study. If adverse events do not improve within 14 days of lowering the dose, the investigational product may be permanently discontinued at the discretion of the treating study physician, participant, and participant's guardian. If a participant exhibits extreme exacerbation of behavioral symptoms (such as self-injurious behavior or aggression) that do not improve substantially following a dose reduction and are determined "probably" or "definitely" related to taking the investigational product, the investigational product may be permanently discontinued sooner than 14 days post-reduction, and the DSMB will be notified. As individuals with ASD often have cyclical changes in behavior independent of medication effects, the study staff will rely on caregivers' experience with the participant to determine if any observed behavior changes are within the expected range for that individual. If the investigational product is stopped permanently, the participant and his caregiver will be asked to complete the remainder of the study visits, return any unused study drug, and repeat safety lab studies.
- If a participant has a seizure while taking the study medication, the study medication will be stopped, and the DSMB will be notified. The participant will be evaluated by the study PI and the participant's primary care physician, treated, and monitored appropriately for the duration of the study. The participant and his caregiver will be asked to return to complete the remainder of the study visits, return any unused study drug, and repeat safety lab studies.

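### The laboratory safety endpoints use the Week 12 draw for everyone, so early stoppers contribute off-drug values and the draw nearest their exposure has no place in the by-arm summary

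*Combined protocol and SAP*

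**What the plan says.** **The endpoint.** Section 3.2 gives the liver tests as "LFTs (Total bilirubin, AST, ALT), actual values and percent change in values from Screening visit to Week 12 visit". CBC, CMP and TSH use the same two visits, and none of them has an exception for participants who have stopped drug. In the same list, vital signs are to be reported at every time point measured as well as by their change to Week 12.

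**The meaning of Week 12.** Section 6.7 states: "The week 12 visit marks the end of the active treatment phase of the study". The schedule of events (Appendix 6A) labels the visit as treatment end and marks safety labs only there and at Screening. The DSMB text in 8.6.1 and Appendix 6B refers to baseline and end-of-treatment labs and has no separate category for a draw taken at stopping.

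**What happens after an early stop.** For the reasons listed in 4.4.1, "every effort will be made to bring the subject in promptly for a clinic visit to perform safety measures, including physical examination and laboratory measures". The same section adds that "study personnel will request that subjects who prematurely stop treatment complete the remaining study visits and procedures as outlined in the protocol". Under 8.5, a participant whose product is stopped permanently is "asked to complete the remainder of the study visits, return any unused study drug, and repeat safety lab studies"; no timing is given for those repeat labs.

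**The analysis.** Section 7 contains no laboratory safety analysis: no on-treatment window, no rule for the last value on drug, and no use for a draw at stopping. Section 7.3 says only, in general terms, that all available data are included.

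**The concern.** A participant who stops early can have two post-baseline laboratory results: one close to the last dose and one at Week 12, after a period off drug. Section 3.2 takes the second and gives the first no role. In the active arm, a value that no longer reflects exposure then stands beside true end-of-treatment values. In the placebo arm there is no drug effect to wash out, so the distortion runs one way, toward no difference between arms.

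The schedule offers no other protection. For participants who stay on drug, Week 12 is the only planned laboratory draw after dosing begins. The by-arm laboratory summary therefore rests on a single visit, and that visit is the wrong one for anyone who has already stopped.

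**Working it through.** The documents state no figure to reproduce. The check sets the sections side by side and then illustrates the size.

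**Step 1: the rules followed as written.** Suppose a participant stops at Week 4.
- 4.4.1 or 8.5: safety labs are sought after stopping, and the remaining visits are requested.
- 6.7 and Appendix 6A: the Week 12 visit includes a safety draw.
- 3.2: the endpoint is the change from Screening to Week 12.

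The value entering the endpoint is taken 8 weeks (56 days) after the last dose. The draw around stopping enters no endpoint. No sentence says outright that off-drug values count as end-of-treatment values; it follows from the fixed visit and the absence of any other rule.

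**Step 2: is the Week 12 value still informative?** Section 1.2 gives a sulforaphane half-life of 1.77 h, so 56 days is 56 × 24 / 1.77 = 759 half-lives. The parent compound is not the right yardstick, though, because 1.2 also says: "Despite the relatively short half-life, SF is believed to have a longer duration of action, as induced phase 2 enzymes have half-lives measured in days". The documents give no exact enzyme half-life, so 2 to 7 days is assumed. Residual effect after t days = 0.5^(t / half-life):

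| Days off drug | Half-life 2 d | Half-life 7 d |
|---|---|---|
| 14 | 0.8% | 25% |
| 28 | 0.01% | 6% |
| 56 | under 0.01% | 0.4% |

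A recent stopper may carry some effect to Week 12; someone who stopped a month or more earlier carries little. The documents give no recovery times for ALT or TSH, so this is indicative only.

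**Step 3: dilution of a mean shift.** Inputs: 27 per arm (7.1); k active participants who have stopped, attend Week 12 and are back to baseline (assumed); the same on-drug effect in all participants. Share of the on-drug mean shift that remains visible = (27 − k) / 27:

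| k | Share shown |
|---|---|
| 1 | 26/27 = 96% |
| 2 | 25/27 = 93% |
| 3 | 24/27 = 89% |
| 4 | 23/27 = 85% |
| 5 | 22/27 = 81% |

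The 15% loss assumed in 7.1 does not supply k. It is loss to follow-up, and a participant who is lost contributes no Week 12 value at all.

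**Step 4: dilution of a count (hypothetical).** If 4 of 27 active participants had an on-drug ALT rise and 2 of them stopped and normalised, Week 12 would show 2/27 = 7.4% instead of 4/27 = 14.8%.

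**The case against.** **Safety oversight does not depend on this endpoint.** A reader might infer that an abnormality which led to stopping and then resolved would be missed completely. The documents do not support that. Section 8.1 makes an abnormal result an adverse event if it leads to withdrawal, needs active management such as discontinuing drug, or is judged clinically significant. Section 8.2 requires all adverse events to be logged, and Appendix 6B sends adverse event forms to the DSMB. This stands and limits the point to the endpoint summary. Adverse event records still do not replace a by-arm comparison of values, and they need not capture shifts within the normal range.

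**The stopping draw is not assured.** A reader might assume that everyone who stops has a prompt draw. Section 4.4.1 ties the prompt visit to listed reasons, which do not name non-serious intolerance, and promises only every effort. Intolerance falls under 8.5, which gives no timing. This stands, so the added summary must allow for a missing or delayed draw.

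**The stopping draw may itself be off drug.** One day after the last dose is 24 / 1.77, or about 14 half-lives. That is correct for the parent compound. On the enzyme timescale in 1.2, however, a draw days after stopping is nearer to exposure than one weeks later. For the same reason, it would go too far to say that a Week 12 value after stopping tells nothing about the drug.

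**The prior ALT and TSH findings are weak.** A reader might take the Phase I results in the clinical background as established drug signals. That section says ALT rose in all participants, placebo included, and was not clearly attributable to the product; one of the three raised TSH values was on placebo. These results are a reason to measure the tests on drug, not evidence of harm.

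**A fixed-visit summary is defensible, and no between-arm laboratory test is planned.** Both statements are fair. They argue for keeping the Week 12 summary, not for leaving the draw nearest exposure unanalysed.

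**Conclusion.** The point holds as a limited, cheaply corrected weakness in the laboratory safety summary. Followed as written, 3.2 counts off-drug values in the active arm and gives the draw nearest exposure no place. Any reversible effect on laboratory values is diluted toward no difference.

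The size cannot be fixed from the documents, which give no rate of early stopping. The 96% to 81% range assumes 1 to 5 stoppers among 27, full return to baseline by Week 12, and equal effects in stoppers and completers. With no stoppers there is no dilution; if stoppers had larger effects than completers, it would be greater. Nothing in the documents shows that stoppers would have abnormal laboratory values, since none of the stopping reasons listed in 4.4.1 is defined by a laboratory result.

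**What to change.** In 3.2, keep the Screening-to-Week 12 summary for all participants and flag each Week 12 value taken after the participant had stopped drug. Add two summaries by arm:

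- **(a) Last value on or nearest to drug:** change from Screening to the last value on drug or, for early stoppers, to the first draw after stopping where one was obtained, with days since last dose shown.
- **(b) Worst post-baseline value:** for each test, including unscheduled draws.

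Report how many early stoppers in each arm had no draw around stopping. This is a change of analysis only: it uses samples the protocol already seeks and alters no dose, visit or stopping rule.

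The cost is one definition and one extra table. The drawback is that time from Screening to the value in (a) varies between participants, which is why the fixed Week 12 summary should stay beside it. For participants who complete treatment with no unscheduled draw, (a) and (b) equal the Week 12 value, so the added table matters mainly for those who stop early.
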